4.5.2. Pharmacokinetics Variables

Blood (plasma) samples will be collected for PK analysis and estimation of DHA exposure parameters. Approximately 10mLs (~2 mL/timepoint) of venous blood will be collected into fluoride-oxalate tubes from the arm opposite of that used for drug administration at pre- and 4 times after the first on-study dose in the hospital during different sampling windows. Sampling windows are defined as 0 (pre-dose), 0-1 hour, 1-2.5, 2.5-4, 4-6 and 6-24 hours post the first on-study dose of IV artesunate. Participants will be randomly assigned to either the 4-6 hour or the 6-24 hour collection timepoint via the Screening and Enrollment Log. All blood samples will be chilled immediately to prevent artesunate degradation by plasma esterases. Samples will be centrifuged within 30 minutes to minimize hemolysis, and aliquots of plasma will be stored at -80°C. Plasma aliquots will be shipped intermittently to the DMID-CMS (i.e., Fisher BioServices) for storage before quantification. Backup samples will be stored at the IDI Core Laboratory. Plasma samples will be analyzed by a validated liquid chromatographic-tandem mass spectrometry (LC-MS/MS) assay with measurement ranging from 1 to 3500 ng/mL (lower limit of quantification [LLOQ] to upper limit of quantification [ULOQ]).

Concentrations of DHA will be measured and used in estimating DHA exposure parameters, including maximum concentration (C_{max}), area under the curve over hours 0-12 (AUC_{0-12}), half-life ($t_{1/2}$) and time to C_{max} (T_{max}).

4.5.3. Safety Variables

Although no safety outcome measures are planned for this trial, the following safety variables will be collected according to the schedule in [Table 2](#):

- The type, incidence, relatedness, and severity of AEs and SAEs will be recorded after study drug administration through the final visit on Day 183 (± 14) or ET on the appropriate data collection form and eCRF.

All AEs will be assessed by the PI or appropriate sub-investigator using the Division of AIDS (DAIDS) Table for Grading of Severity of Adults and Pediatric Adverse Events. For unsolicited events not included in the DAIDS Table, the following guidelines will be used to quantify intensity:

- Mild (Grade 1) – events require minimal or no treatment and do not interfere with the participant's daily activities.
- Moderate (Grade 2) – events result in a low level of inconvenience or concern with the therapeutic measures. Moderate events may cause some interference with functioning and daily activities.
- Severe (Grade 3) – events interrupt a participant's usual daily activity and may require systemic drug therapy or other treatment. Severe events are usually incapacitating.
- Blood samples for biochemistry and hematology assays will be collected according to the schedule in [Table 2](#).
 - Serum biochemistries will be examined on site using a COBAS C111 Analyzer. Biochemistry variables will include serum lactate, serum bicarbonate, creatinine, blood urea nitrogen (BUN), alanine aminotransferase (ALT), aspartate aminotransferase (AST), direct bilirubin, total bilirubin, calcium, sodium, potassium, and glucose. Note that some biochemistry variables will be utilized in the PD analysis.

- Full blood count will be measured with a Haematology – Mindray Shenzhen analyzer. Hematology variables will include hemoglobin, platelets, white blood cell (WBC) count, neutrophil count, and neutrophil %. Note that some hematology variables will be utilized in the PD analysis.
- Dipstick urinalysis will be performed according to the schedule in [Table 2](#). A variety of analytes will be measured, including urine protein, urine glucose, pH, urobilinogen, bilirubin, nitrites, leukocyte esterase, ketones, and hemolyzed and non-hemolyzed blood.
- Vital signs will be collected approximately every 6 hours until parasite clearance, and will include axillary temperature, respiratory rate, systolic and diastolic blood pressure, and pulse.
- Complete physical examinations will be performed at Screening, Enrollment, and Day 2, Day 3, Day 4, Day 5, Day 6, Day 7 (± 2), and Day 183 (± 14). Targeted physical examinations will be performed as needed on Day 14 (± 2) and Day 28 (± 4) and at early termination visits.

5. SAMPLE SIZE CONSIDERATIONS

A maximum of 100 participants will be enrolled in the study. This maximum of 100 participants would provide sufficient sample size to achieve precision on PK parameters following the FDA pediatric precision criteria for conducting PK studies (achieving a 95% confidence interval (CI) within 60% and 140% of the geometric mean).

Simulations in R version 3.4.2 were used to explore power to detect simple linear relationships between exposure and response in the analysis of the primary objective with the planned sample size. The primary objective of this study is to determine the relationship between DHA exposures after IV dosing and markers of physiologic dysfunction associated with severe malaria. This objective can be framed as a series of statistical hypothesis tests, each evaluating the effect of the DHA exposure parameter on the marker of physiologic dysfunction measured at a specific timepoint, adjusting for covariates. The null hypothesis is that there is no effect of exposure on response, and the alternative hypothesis is that there is an effect.

Because the primary objective of this study encompasses multiple exposure and response variables, and the response variables are measured at multiple timepoints, there are multiple exposure-response relationships that are of interest (one for each unique combination of exposure variable, response variable, and timepoint). Thus, there is a need to control type I error. As this study is exploratory (hypothesis-generating) rather than confirmatory, Benjamini-Hochberg procedure is used to control the false discovery rate at 0.05 [Table 5].

For a multiple hypothesis test, average power is defined as the proportion of false null hypotheses correctly rejected [6]. Table 3 provides the average power computed from 5000 simulations, varying the following quantities:

- Number of total statistical tests, representing the number of combinations of exposure variable, response variable, and timepoint to be tested in support of the primary objective
- Value of R^2 for the true, non-null exposure-response relationships
- Proportion of tests with true, non-null exposure-response relationships with the specified R^2
- Sample size

Sample sizes considered in these simulations included 100 or 80 participants. These original simulation results indicate that the target sample size of 100 participants provides >90% power for detecting simple linear relationships for 24 or 48 tests with an underlying R^2 of at least 0.2, if the proportion of non-null relationships among those tested is at least 5%. If at least 80 participants complete follow-up for the primary outcome measure, power for the same scenario is approximately 88%.

However, at the end of the planned enrollment period of 6 months, only 46 participants had been enrolled in the study. Further simulations were performed under the same settings described above with smaller sample sizes considered. These results are also provided in Table 3. These simulation results indicate that if at least 70 participants complete follow-up for the primary outcome measure, power for detecting simple linear relationships for 24 or 48 tests with an underlying R^2 of at least 0.2, if the proportion of non-null relationships among those tested is at least 5%, is $\geq 80\%$.

Additionally, given that there are eleven markers of physiological dysfunction, four exposure parameters, and four timepoints (see Section 8.1) of interest, the total number of possible hypothesis tests for all of these relationships is 176. Further simulations were performed under the same settings described above with 176 tests and sample sizes of 75, 80, or 90 participants considered. These results are also provided in Table 3. These simulation results indicate that if at least 75 participants complete follow-up for the primary outcome

measure, power for detecting simple linear relationships for 176 tests with an underlying R^2 of at least 0.2, if the proportion of non-null relationships among those tested is at least 5%, is greater than 80%.

6. GENERAL STATISTICAL CONSIDERATIONS

6.1. General Principles

Unless otherwise specified, continuous variables will be summarized by the following descriptive statistics: the number of participants with non-missing data included in the analysis (n), mean, standard deviation (SD), median, minimum value (Min), and maximum value (Max). Summary statistics for discrete data will include frequencies and proportions.

6.2. Timing of Analyses

The primary data analysis will occur after all primary and secondary outcome measure data is collected, with time of hospital discharge response outcome measures censored at Day 183 (± 14). Results of this primary data analysis will be available for public release. Results of the primary and secondary data analyses will be included in an interim CSR once all primary and secondary study outcome measures are reached at Day 183 (± 14). Available results of exploratory analyses may be included in the interim CSR provided the SAP addendum including these analyses is finalized at the time of the interim CSR, and all other exploratory analyses will be included in a CSR addendum(s).

6.3. Analysis Populations

All analysis populations to be used in the final analysis are described in this section. The primary analysis will be performed using the PD Analysis Population. Estimation of population PK parameters included in the primary analysis will be performed using the Population PK Analysis Population. Other analyses may use the Safety Population, PD Analysis Population, or Population PK Analysis Population.

6.3.1. Safety Population

The Safety Population will include all participants who received at least one dose of IV artesunate.

6.3.2. Population Pharmacokinetic Analysis Population

The Population PK Analysis Population will consist of all participants who received at least one on-study dose of IV artesunate and for whom DHA concentration data are available.

6.3.3. Pharmacodynamic Analysis Population

The PD Analysis Population will include all participants meeting the definition of severe malaria at enrollment for which exposure parameters can be estimated from the final population PK model and for which post-baseline response data are available.

6.4. Covariates and Subgroups

Sensitivity analyses for the primary and both secondary analysis outcome measures will be conducted to assess the effect of receipt of IV artesunate or other artemisinin-based therapies before enrollment on results of the primary and secondary analyses. This sensitivity analysis will be conducted on the subset of the PD Analysis Population who did not receive any IV artesunate or other artemisinin-based therapy before enrollment.

Otherwise, the protocol does not define any formal subgroup analyses, and the study is not adequately powered to perform subgroup analyses. However, primary and secondary analyses will be adjusted for

possible confounding factors. The following baseline covariates will be considered for inclusion in all primary and secondary analyses:

- Sex (male or female),
- Weight group (<20 kg or \geq 20 kg),
- Receipt of IV artesunate or artemisinin-based therapy before study enrollment (received no IV artesunate or artemisinin-based therapy before study enrollment or received any IV artesunate or artemisinin-based therapy before study enrollment), and
- Receipt of antimalarial concomitant medications or other concomitant medications with antimalarial properties (received no such concomitant medications or received any such concomitant medications).

Receipt of oral ACT post-enrollment (received no oral ACT or received any oral ACT) will also be considered for inclusion as a covariate in primary analyses at timepoints at which there are participants receiving oral ACT and in secondary analyses. The number of doses of oral ACT received may also be considered for inclusion in these analyses.

Inclusion of covariates in each primary and secondary analysis will be informed by exploratory boxplots and stacked bar graphs of response variables by covariate values, and by timepoint when appropriate (see Section 8 for further details).

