All screening tests, medical history and examinations will be performed only after study consent/assent where applicable is obtained. If an individual's medical chart or results diagnostic tests performed as part of an individual's medical care are going to be used for screening, written informed consent must be obtained before review of that information.

An eligibility checklist will be prepared for each participant and will later become part of the source document for participants enrolled in the trial. A unique identification number will be assigned to each study participant. A medical history will be taken. Concomitant medications will be documented. Physical examination (including Blantyre coma score (BCS)) and laboratory

screening tests will include: hemoglobin, platelets, white blood cell (WBC) count, neutrophil count; serum lactate, bicarbonate, blood urea nitrogen (BUN), calcium, creatinine, glucose, alanine aminotransferase (ALT), aspartate aminotransferase (AST), total and direct bilirubin, sodium, and potassium; and urinalysis. Laboratory testing will be performed at the Lancet laboratory at the study site and at a local reference laboratory if needed. Results obtained within 24 hours prior to enrollment can be included as baseline labs and would satisfy both screening and enrollment/baseline labs. A thick and thin blood smear will be performed for estimation of parasite density. A dried blood spot specimen will be collected for artemisinin resistance assessment. A blood specimen will be collected in a PAXgene tube for *P. falciparum* gene expression analysis. Recruitment will continue over a single malaria transmission season until up to 100 eligible participants have fulfilled all the inclusion criteria and none of the exclusion criteria.

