The secondary outcome response variables are time to hospital discharge, and measures of parasite clearance calculated from parasite density, as measured by thick blood smear such as parasite clearance half-life, total parasite clearance by Day 2, and time to 90% reduction in parasitemia. Parasite clearance half-life (PCT₅₀) and time to 90% reduction (PCT₉₀) will be estimated using the WorldWide Antimalarial Resistance Network (WWARN) parasite clearance estimator (PCE) algorithm (Flegg 2011). The relationship between AUC_{0-12} and C_{max} and the time-to-event response variables will be analyzed using Cox proportional hazards regression.

The relationship between AUC_{0-12} and C_{max} and the binary variable of total parasite clearance by Day 2 will be analyzed using logistic regression. Covariates will include exposure and potential confounding variables. The full list of covariates to be considered and the variable selection strategy will be described in the SAP. Analyses of secondary outcome variables will not be adjusted for multiplicity.

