4.4.3. Method of Assigning Participants to Treatment Groups (Randomization)

This is a non-randomized study in which all participants, once consent is obtained and eligibility is confirmed, will receive IV artesunate. Dosage will be assigned based on participant weight. Enrollment will be done online using the enrollment module of the Statistical Data Coordinating Center's (SDCC) Internet Data Entry System (IDES).

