6.5. Missing Data

Every effort will be made to minimize missing data and collect all outcome measures specified in this protocol. Participants who discontinue treatment will be followed after treatment discontinuation for collection of all scheduled follow-up data with their consent.

Missing dose data (dosing time, or dosing date) will be imputed to maximize the inclusion of observations subsequent to doses with missing information. Missing dosing time will be imputed if the dose date and amount are available:

- If dosing times are missing, the pre-dose sample time combined with the dose number and dosing timeline will be used to determine the pre-study and on-study dosing times.
- Dosing time will be imputed as the mean of the time from pre-dose draw to dosing for those not missing the given sampling window.

Missing covariate data for analyses that incorporate confounding covariate variables will be handled in the following manner. The covariate will be excluded from the analysis if more than 20% of the covariate values are missing. Baseline individual covariates, including sex and weight group, will be determined from the Day 1 visit. If an individual's baseline covariate is missing at the Day 1 visit, the baseline covariate value will be taken from either the pre-study (screening) visit or from the earliest post-dose visit, whichever is closest to the baseline visit. Receipt of IV artesunate or artemisinin-based therapy before enrollment will be determined from treatment administration records with dates and times before the first on-study dose and/or concomitant medication records with dates up to the Day 1 visit. Receipt of oral ACT, which has planned collection occurring after baseline, will be determined from all visits up to and including the visit at which the analysis timepoint occurs.

No imputation will be performed for missing primary or secondary PD outcome response variables. Rather, only participants in the PD Analysis Population with the PD outcome response variable measured at the timepoint of interest will be included in PD analyses of that PD outcome response variable measured at the timepoint of interest.

Please refer to the Pharmacometrics Analysis Plan for details pertaining to methods for missing concentration data and other missing data that would affect the PK analysis.

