8. PHARMACODYNAMICS EVALUATION

All model-based primary and secondary PD analyses will adjust for a subset of the following covariates: sex, weight group (<20 kg or \geq 20 kg), receipt of IV artesunate or artemisinin-based therapy before enrollment, and receipt of concomitant medications. Where appropriate, primary and secondary PD analyses may also adjust for receipt of oral ACT. Exploratory boxplots and stacked bar graphs of response variables by covariate values, and by timepoint when appropriate, will inform covariate selection for each model.

Primary and secondary analyses will be performed using the Pharmacodynamics Analysis Population, and a sensitivity analysis will be performed for each primary and secondary analysis including only participants who did not receive IV artesunate or other artemisinin-based therapy before enrollment.

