Table 22: Model Specifications for Assessments of Relationships between Time to Hospital Discharge and Exposure Parameters by Exposure Parameter and Analysis Population

[Implementation Note: Model Type will Cox Proportional Hazard. Covariates Included in the Model will at minimum include Exposure Parameter and Actual Time of Collection, but may also include Sex, Weight Group, Receipt of IV Artesunate or Other Artemisinin-Based Therapy Before Enrollment, Receipt of Concomitant Medications, and Receipt of Oral ACT.]

Analysis Population	PK Exposure Parameter	Model Type	Covariates Included in the Model
PD Analysis Population (N=X)	AUC ₀₋₁₂ (N*=X)		
	C _{max} (N*=X)		
	T _{max} (N*=X)		
	t _{1/2} (N*=X)		
PD Analysis Population, No Prior IV Artesunate or Other Artemisinin-Based Therapy Subset (N=X)	AUC ₀₋₁₂ (N*=X)		
	C _{max} (N*=X)		
	T _{max} (N*=X)		
	t _{1/2} (N*=X)		

Notes: N = Number of participants in each analysis population or subset for which time to first hospital discharge can be calculated. N* = Number of participants in each analysis population or subset with estimable PK exposure parameter and for which time to first hospital discharge can be calculated.

Time of hospital discharge is calculated as the time in days from time of initial participant admission to the time of first discharge.

Table 23: Parasite Density Summary Statistics by Timepoint and Analysis Population

Analysis Population	Planned Timepoint ^a	N	Parasite Density (# Parasites per 200 WBC)			
			Mean	SD	Median	Min, Max
PD Analysis Population	0 (0-2) h	x	xx.xx	xx.xx	xx.xx	xx.x, xx.x
	6 (4-8) h	x	xx.xx	xx.xx	xx.xx	xx.x, xx.x
	12 (10-14) h	x	xx.xx	xx.xx	xx.xx	xx.x, xx.x
	24 (22-26) h	x	xx.xx	xx.xx	xx.xx	xx.x, xx.x
	36 (34-38) h	x	xx.xx	xx.xx	xx.xx	xx.x, xx.x
	48 (46-50) h	x	xx.xx	xx.xx	xx.xx	xx.x, xx.x
	Day 3	x	xx.xx	xx.xx	xx.xx	xx.x, xx.x
	Day 4	x	xx.xx	xx.xx	xx.xx	xx.x, xx.x
	Day 5	x	xx.xx	xx.xx	xx.xx	xx.x, xx.x
PD Analysis Population, No Prior IV Artesunate or Other Artemisinin-Based Therapy Subset	0 (0-2) h	x	xx.xx	xx.xx	xx.xx	xx.x, xx.x
	...					

Notes: N = Number of participants in the analysis population or subset with parasite density results available at the respective timepoint.

^a Timepoints are given post-first on-study dose of IV artesunate.

Table 24: Proportions of Total Parasite Clearance by Timepoint and Analysis Population

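### The discharge Cox and Day-2 clearance models omit baseline parasite density and illness severity although DHA exposure is not randomized, so confounding of unknown size and direction cannot be ruled out

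*SAP*

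**What the plan says.** Protocol 11.3.5 commits the secondary models to adjusting for potential confounders and passes the detail on: "The full list of covariates to be considered and the variable selection strategy will be described in the SAP". SAP 6.4 answers: "The following baseline covariates will be considered for inclusion in all primary and secondary analyses". The four items are sex, weight group, artemisinin therapy before enrollment, and concomitant drugs with antimalarial activity. Oral ACT after enrollment may be added.

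SAP 8 repeats the list ("All model-based primary and secondary PD analyses will adjust for a subset of the following covariates") and chooses the subset from plots of response against the listed covariates, so an unlisted variable has no route in. The shells for Table 22 (discharge) and Table 28 (Day-2 clearance) add only collection time: "Covariates Included in the Model will at minimum include Exposure Parameter and Actual Time of Collection, but may also include Sex, Weight Group". The formulas and code in SAP 8.2.1 and 8.2.2 contain exposure and these covariates, with no baseline term.

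The primary models differ. In SAP 8.1 each includes the marker's own baseline value, and Protocol 11.3.5 asks the SAP to deal with baseline–exposure associations for the primary outcome. SAP 15 gives no reason for treating the secondary models otherwise.

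On allocation, SAP 4.4.3 states: "This is a non-randomized study in which all participants, once consent is obtained and eligibility is confirmed, will receive IV artesunate". On data, Protocol 7.1 states: "A thick and thin blood smear will be performed for estimation of parasite density". It also lists BCS and lactate among the screening assessments.

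**The concern.** Every child is on the same weight-based regimen, so differences in DHA exposure arise from the child and not from random assignment. Protocol 11.3.4 itself notes that earlier population PK models did not describe DHA in critically ill malaria patients. If sicker or more heavily infected children have different exposure, exposure also carries prognosis. The hazard ratio in Table 21 and the odds ratio in Table 27 would then be shifted, in either direction, and their 95% intervals would miss the true value too often.

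The listed covariates do not close this gap. Weight group and prior therapy are not severity measures, and oral ACT is post-baseline and reflects recovery. The one planned sensitivity analysis, in children without prior artemisinin therapy, answers a different question. SAP 2.1 says the study is meant to inform dosing regimens, so a shifted exposure effect would matter.

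**Working it through.** **Plan's own figures.** The documents give no power, event count or effect size for these two models. SAP Table 3 covers only the primary tests. All 26 of its cells that were checked reproduce within 0.02 (24 tests, 5% non-null, N=100: 0.954 against 0.95), but this point does not depend on them.

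**Starting density and the Day-2 cut.** Inputs from the SAP are the detection limit of 40/µL (8.2.2) and the 50-h cut (4.5.1, 8.2.2). The half-lives are assumed. With log-linear clearance and no lag, time to clear = log2(P0/40) × half-life. For P0 = 500,000/µL, log2(12,500) = 13.61, which gives:
- 2.5 h: 34.0 h
- 3 h: 40.8 h
- 3.5 h: 47.6 h
- 4 h: 54.4 h

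At 4 h, the density that just clears by 50 h is 40 × 2^(50/4), about 232,000/µL. Starting density can therefore decide the outcome by itself, but only when clearance is slow.

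**Discharge Cox model, no true effect.** Assumptions: severity is standard normal, exposure has correlation ρ with it, discharge times are exponential, and there is no censoring. Adjustment uses two covariates, each correlated r with severity. There were 1,500 trials per cell. N=80 is one of the Table 3 scenarios. N=46 comes from SAP 5, which says that at the end of the planned enrollment period "only 46 participants had been enrolled in the study". Entries are the percentage of 95% intervals that miss the truth, with severity HR 0.5 per SD:

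| | ρ=0.2 | ρ=0.3 | ρ=0.4 |
|---|---|---|---|
| Mean unadjusted HR | 0.89 | 0.85 | 0.80 |
| N=80 unadjusted | 15–17 | 26–30 | 47 |
| N=80 adjusted, r=0.7 | 8 | 10 | 12 |
| N=80 adjusted, r=0.5 | 11 | 15 | 26 |
| N=46 unadjusted | 10 | 17–18 | 28–29 |
| N=46 adjusted | 7–8 | 8–12 | 11–16 |

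- At ρ = −0.3 the mean HR is 1.19. At ρ = 0 the miss rate is 4–7% throughout.
- With severity HR 0.7, the unadjusted rates are 10/13/21% (N=80) and 7/9–10/13–14% (N=46). Adjusted rates are 7–12% and 6–9%.
- With weak proxies (r=0.3, N=80, HR 0.5), 22–26% still miss at ρ=0.3 and 39% at ρ=0.4.
- With ρ = 0, severity HR 0.5 and a true exposure HR of 1.4, the unadjusted estimate is 1.30 and the adjusted one 1.35–1.38. Power rises from 58–60% to 67–73% at N=80.

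**Day-2 logistic model.** Assumptions: log10 density is normal (mean 4.7, SD 0.7) and half-life is lognormal (log-SD 0.25). A child counts as cleared if clear by the 48-h smear, taken uniformly over 46–50 h. With no true effect and a correlation of 0.3 between density and exposure, the miss rates at median half-lives of 3/3.5/4 h are 12/20/23% (N=80) and 8/12/15% (N=46) without density. With density they are 2–5%.

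**Power for Day-2 clearance at zero correlation, nobody pre-dosed.** Clearance under no effect is 98/92/82/69% at 2.5/3/3.5/4 h. Expected non-clearers are therefore 80 × (0.02, 0.08, 0.18, 0.31) = 1.6, 6.4, 14.4 and 24.8 at N=80, and 0.9, 3.7, 8.3 and 14.3 at N=46. Adding density changes power as follows:
- N=80: 34 to 27, 44 to 48, 61 to 70 and 68 to 80%.
- N=46: 19 to 10, 25 to 23, 37 to 40 and 43 to 54%.

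**Children dosed before enrollment.** SAP 4.5.1 times smears from the first on-study dose, but the 50-h cut runs from the first dose. For a child first dosed more than 4 h earlier, even the start of the 46–50 h smear window falls after the cut (46 + 4 = 50). On this clock with 60% pre-dosed, two separate runs at N=80 (3/3.5/4 h) gave power of 51 to 46, 63 to 61 and 69 to 66%, and 49 to 48, 66 to 66 and 67 to 67%. At N=46 it was 29 to 19, 38 to 35 and 42 to 42%. Bias control survived: at N=80 and correlation 0.3, miss rates fell from 13–25% to 4–5%.

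**The case against.** The strongest reply is that nothing here is demonstrated. The documents contain no exposure–severity correlation, no prognostic strength and no final N, and the larger figures need severity HR 0.5 together with a correlation of 0.3–0.4. At a correlation of 0.1, unadjusted intervals miss 6–9% of the time and adjusted ones 5–8%. These are secondary outcomes in a study that SAP 5 calls exploratory, and Tables 21 and 27 show estimates and intervals without p-values. All of this stands, and it limits the weight of the point. A reader might infer that the secondary results are biased, or biased in a known direction. The documents do not support that.

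A second reply is that the simulated models are simpler than the SAP's: they leave out collection time and most listed covariates. This also stands. In sparse data the cost is then higher: with three extra binary covariates at N=46 and a 3-h half-life, the density model failed to fit in 31% of runs, against 2% without them.

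A reader might also infer that adding density buys power. When non-clearers are few or many children are pre-dosed, it does not.

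Finally, the PCT50 and PCT90 models use the same covariate list. Those outcomes come from the clearance slope (SAP 8.2.2), so starting density does not enter them in the way shown above, and this point does not extend to them.

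None of this supplies a reason for the omission. The SAP says it adjusts for possible confounders, the values are already collected, and covariates added after lock would be post hoc.

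**Conclusion.** The omission is confirmed in SAP 6.4, SAP 8, the model text and code in 8.2, and Tables 22 and 28. What follows from it is a possibility of confounding, of unknown size and sign. Under the assumed inputs at N=80, interval miss rates range from nominal at zero correlation to 47% for the discharge model, and reach 23% for Day-2 clearance at a correlation of 0.3. Adjustment restores roughly nominal error for Day-2 clearance. For discharge it removes only part of the excess, and little if the markers are weak proxies for severity. The benefit for Day-2 clearance is bias control, not power. The gap should be closed before database lock, with medium confidence in how much it matters.

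**What to change.** - In SAP 6.4 and 8.2, pre-specify log baseline parasite density in the Day-2 logistic model. In the discharge Cox model, pre-specify log baseline density plus one severity marker, baseline lactate or BCS, named before lock. A count of severe-malaria signs would serve poorly, because SAP 3.3 lets investigators stop assessing once the definition is met.
- Report each result beside the model without these terms, and amend the notes to Tables 22 and 28.
- Define baseline for both density and the severity marker by the SAP 3.3 rule: the last value before the first IV artesunate dose, otherwise the value closest to it. SAP 3.3 does not name parasite density. SAP 6.5 says "Baseline individual covariates, including sex and weight group, will be determined from the Day 1 visit", and Protocol 8.1 has Day 1 biochemistry drawn at least 12 hours after the screening sample, so a Day 1 lactate may be post-dose. State that the SAP 3.3 rule replaces the Day 1 rule for these covariates.
- Use a penalized logistic fit if non-clearers are too few for a stable fit.
- State in the report that residual confounding remains.

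The cost is SAP text and 1 (logistic) or 2 (Cox) degrees of freedom, with no new data. Day-2 power may not improve, or may fall, when non-clearers are few (34 to 27% at N=80 and 2.5 h, or 34 to 31% with a penalized fit) or when many children are dosed before enrollment. Under SAP 6.5 a covariate with more than 20% missing values would still be dropped.
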